Any possible bioeffects that may be caused by SWE imaging with CIO will be monitored and determined by liver function test (LFT), with results graded according to the NCI scale for drug hepatotoxicity (grade 1 = 1-3x upper limit of normal; grade 2 = 3-5x upper limit of normal; grade 3 = 5-20x upper limit of normal; grade 4 = >20x upper limit of normal). Participants will attend study visits to obtain blood samples collected 1 day post-scanning, 2 days post-scanning, and 7 days post-scanning to trend liver function tests and assess laboratory value normalization.

d) Adverse event reporting guidelines

The PI will be responsible for safety monitoring of enrolled subjects during the study period. Subjects will be evaluated for signs of pain and discomfort before, during, and immediately after the study visit. Any significant adverse event will be reported to the IRB and followed up by the study staff.

All Adverse Events, Serious adverse events, Adverse Device Effects, and Device Deficiencies will be collected at the time of reporting by the subject or when detected by the Investigator. They will be source documented and maintained as part of the study record.

An assessment of the following metrics will be made by the Investigator for each Adverse Event:

- severity,
- seriousness,

- anticipated or unanticipated,
- relation to study participation or investigational imaging technique,
- action taken,
- outcome (resolution, sequelae, etc.)

Definition of adverse events (AE) in this study will be "any untoward or unfavorable medical occurrence in a human subject, including any abnormal physical exam or certain unexpected abnormal laboratory finding, symptom, or disease, temporally associated with a subject's participation in the research".

Definition of serious adverse events (SAE) in this study:

A SAE is any AE that:

Results in death, or

Is life-threatening, or

Results in hospitalization or prolongation of existing hospitalization, or

Results in a persistent or significant disability/incapacitation, or

May jeopardize the participant's health and may require medical or surgical intervention to prevent one of the other outcomes listed above. No SAEs are anticipated in this study.

All AEs will have their relationship to study procedures assessed by the PI. The following criteria will be used to identify causality; (0) Not related, (1) Unlikely to be related, (2) Potentially related, (3) Probably related, (4) Definitely related. PI will be responsible for determining whether an adverse event (AE) is expected or unexpected in this study. An AE will be considered unexpected if the nature, severity, or frequency of the event is not consistent with known ultrasound risks and complications, which are very limited. The occurrence of an AE or SAE may come to the attention of study personnel during ultrasound scans. Any medical condition that is present at the time that the participant is included will be considered as baseline and not reported as an AE. However, if the study participant's condition deteriorates at any time during the study, it will be recorded as an AE.

The following will be reported in the case report forms for each Device Deficiency that occurs:

- device ID,
- device event description,
- date of deficiency,
- whether the deficiency caused or could have caused an Adverse Device Effect to occur.

The disposition of all safety events, assignment of relatedness, and determination of seriousness is the responsibility of the Investigator. All Adverse Events will be reported in the final Clinical Study Report for this study.

The Investigator is responsible for reporting the event to the approving IRB as dictated by the guidelines defined by the IRB and, if applicable, regulatory authorities. Additionally, the Investigator will report to the sponsor and regulatory authorities as required by national regulations.

The principal investigator will review adverse events on an individual basis, the subjects will have the phone numbers of the research team and a 24-hour phone number to call in the case of any adverse events.

11. Privacy and Confidentiality

- Study procedures will be conducted in a private setting
- Only data and/or specimens necessary for the conduct of the study will be collected
- Data collected (paper and/or electronic) will be maintained in a secure location with appropriate protections such as password protection, encryption, physical security measures (locked files/areas)
- Specimens collected will be maintained in a secure location with appropriate protections (e.g. locked storage spaces, laboratory areas)

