In this study, we aim to assess possible bioeffects that may be caused by the use of SWE with conditionally increased acoustic output pressure (CIO). Bioeffects will be monitored by a series of liver function tests (LFTs) with results graded according to the NCI scale for drug hepatotoxicity. LFTs will be collected prior to SWE imaging using CIO, as well up to 7 days post-imaging. Results will be compared to LFTs collected from the same patient after a washout period followed by standard SWE imaging. Secondarily, we aim to understand the degree to which SWE imaging results have improved with the use of COI.

[figure not shown]

Figure 1A. Standardized MI and TI display (red area) Ultrasound systems meeting the U.S. FDA 510(k) guidance for 'Track 3' systems will display TI and MI values on the ultrasound image. Figure 1B. Unreliable SWE measurement with high SCD value. Figure 1C, 1D: Poor region of interest (ROI) filling due to poor shear wave propagation. High skin to liver capsule distance may be an important factor for poor ROI filling.

b) Rationale behind the proposed research, and potential benefits to patients and/or society

As the use of the SWE, is a non-invasive, low-cost and widely available imaging diagnostic tool for liver fibrosis staging, and the acoustic and thermal limits in current FDA guidelines typically do not give reliable SWE measurements in obese patients with high skin-to-liver capsule distance

(SCD), our aim is to conditionally increase the acoustic pressure (CIO) of a SWE system to help clinicians obtain accurate SWE results in obese patients. We aim to reduce the need for monitoring hepatic fibrosis and steatosis using liver biopsy, as it is and costly, invasive with high morbidity and mortality rates, and is subject to sampling error.

2. Specific Aims and Objectives

Aim 1: Ascertain if hepatic bioeffects occur when increasing acoustic output above FDA limits for SWE imaging.

[figure not shown]
Aim 2: Determine if SWE image quality improves when using increased acoustic output.

Aim 3: Quantify the effect of phase aberration on SWE tracking.

Hypothesis: Increased acoustic output will improve SWE image quality without causing hepatic bioeffects.

3. General Description of Study Design

This is a prospective pre/post single arm non-inferiority study to show that the increase in liver function tests following increased acoustic output SWE is not more than two standard deviations.

4. Subject Selection

a) Inclusion criteria

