The first study visit is expected to take approximately 45 minutes. This will occur within 48 hours of the screening visit blood sampling and may occur on the same day as the screening visit. Subjects will fast for 4 hours prior to the exam. Subjects will then undergo a conventional standard of care ultrasound SWE exam of the liver and a repeat exam with increased acoustic output. The standard SWE exam consists of 10 diagnostic elastography measurements in the right lobe of the liver via an intercostal window during suspended respiration. If non-diagnostic values are obtained, repeat acquisitions are attempted up to a total of 20 imaging attempts. For increased acoustic output, the operator will set the mechanical index (MI) value of 2.9, 10 SWE measurements will be repeated in a similar fashion, with 20 acquisition attempts allowed. Additional standard clinical B-mode ultrasound images (within FDA energy deposition limits) will be obtained while capturing raw RF data.

Study Visits 2, 3, 4:

Participants will undergo blood sampling of 10mL or less (1 specimen container – less than 90mL) for liver function testing 1 day after visit 1, 2 days after visit 1, and 7 days after visit 1.

Phone Follow Up Visit:

Within 1 week following study Visit 4, the study team will contact subjects by phone for the completion of a final questionnaire (to be completed by study staff) to obtain information regarding alcohol consumption, change in medical history, and adverse events.

b) Devices and imaging procedures

A commercial curved abdominal ultrasound probe GE C1-6 will be used. The software version of the device will be R2.5.2NeatG. An MI of 2.9 will be used for CIO.

Staff will assess the probe's individual channel sensitivity profile to ensure adequate functionality using the electronic probe assessment tool (E-PAT). E-PAT testing will be performed 1) after imaging each subject and 2) at least once within 14 days prior to each subject (if not already performed), including the initial subject. Additional testing may be performed if there are any concerns of probe malfunction (i.e. accidental probe drop).

c) Data to be collected and when the data is to be collected

	Prescreening	Screening	V1	V2	V3	V4	Phone F/U
Fits within Screening Age**	X						
Demographics [#]		X					
Social Security Number*		X					
Height/Weight	X						
Medication Stability [@]	X						
Medication List and Dose ^{\$}		X					
Liver Disease History [%]	X						

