Concurrent Clinical Trial Participation	X						
Chemotherapy Screening	X						
Pregnancy Screening	X						
Implantable Electronic Device Screening	X						
Alcohol Consumption	X						
Ultrasound Contrast Exposure Screening	X	X	X				
Acute Illness / Symptoms	X	X	X				X
Change in Medications			X				X
Change in Alcohol Consumption		X	X				X
Change in Medical history		X	X				X
Liver Function Testing		X		X	X	X	
Serum bHCG [^]		X					
Conventional SWE			X				
Increased acoustic output SWE			X				

**yes/no response to inclusion/exclusion age criteria

[#]age, date of birth, sex, race/ethnicity

^{*}for Advarra compensation

[@]change in medication over last 30 days and expected change over next 30 days

^sprescription, over-the-counter, herbal/dietary supplements

[%]transplantation, viral hepatitis, abnormal prior LFTs

[^]for women of child bearing potential

d) Result Reporting

Liver function testing results will be accessible to subjects through patient gateway. Subjects will be contacted by the study team for lab values higher than 3x the laboratory upper limit of normal. Positive pregnancy testing will be reported to subjects.

The results of the SWE exams are not planned to be shared as the interpretation of the SWE values requires clinical correlation. Furthermore, exams may be performed by research staff who are not credentialed at MGH to perform clinical ultrasound elastography scanning. As a result, image quality may not meet clinical standards which may reduce the reliability of SWE results. Results from increased acoustic output SWE will not be released as this technique is experimental and the results have not been correlated with histopathology.

e) Incidental Findings

Should incidental findings, imaging or otherwise, of perceived clinical significance be identified, the research team will contact the subject to inform them of the finding. Permission to contact the subject's primary care physician will be obtained prior to communicating results for continuity of care.

f) Study Termination Criteria

Subjects with baseline liver function testing values greater than 3x the laboratory upper limit of normal or with a positive serum pregnancy test will not undergo increased acoustic output imaging or follow up liver function testing. We will attempt to contact non-responding subjects for a period of 4 weeks after enrollment, at which point, they will be deemed 'lost to follow up'.

g) Remuneration

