Following the completion of Study Visits 1, 2, 3, and 4, as well as the follow-up phone call, subjects will receive \$150 total by card using the Advarra participant payment system, divided into the following increments, given after each visit:

- Screening Visit: \$15 and parking voucher
- Study Visit 1: \$40 and parking voucher
- Study Visit 2: \$15 and parking voucher
- Study Visit 3: \$15 and parking voucher
- Study Visit 4: \$15 and parking voucher
- Completion of all study components: \$50

A participant is considered to have completed this study if the scheduled scan has been performed, and all requested demographic, clinical history, LFT blood test results, and anthropometric information has been collected.

h) External Data Sharing

De-identified laboratory, clinical, and imaging data will be shared with the study sponsor via the MGH Secure File Transfer service.

7. Risks and Discomforts

a) Complications of surgical and non-surgical procedures.

Conventional ultrasound is painless, non-invasive, and does not require the administration of ionizing or X-ray radiation. Subjects may experience minor discomfort from needing to remain still, the pressure of the ultrasound probe, or the need for repeated breath holding.

The risks associated with elevated MI ultrasonic imaging include thermal and non-thermal bioeffects. Non-thermal risks associated with elevated MI imaging are related to the potential for inducing cavitation. *A recent AIUM report concluded that exceeding the recommended maximum MI given in the FDA guidance (i.e., 1.9), up to an estimated in situ (effective MI, MIE) value of 4.0, could be justified without concern for increased risk of cavitation in tissues without gas bodies if there were a clinical benefit[21]. Since there are no endogenous sources of air in the liver, and these studies will be performed on patients that have not had ultrasound contrast agent in the previous 24 hours, and because the measured MI values will be kept ≤ 3.0 - which, conservatively, should keep the in situ value, MIE, ≤ 4.0 , the potential for cavitation is very small. If, however, it were to occur, the likely impact of the resulting tissue damage would be limited given the large mass of the liver relative to the small volume of the insonated tissue. Thus, it is unlikely that clinically significant liver damage would result, if any at all.*

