There are no expected direct benefits to the subjects participating in the study. Liver biopsy, the current gold standard test to assess fibrosis is imperfect, costly, invasive, and subject to sampling error. The imaging strategy that will be evaluated, increased output SWE, has the potential to reduce the number of liver biopsies performed for the diagnosis and monitoring of hepatic fibrosis and steatosis. Patients, particularly those who are obese, may potentially benefit in the future by having a better non-invasive test to stage their liver fibrosis and thus, may be spared more invasive testing.

9. Statistical Analysis

Three biomarkers based on liver function test which are associated with liver injury are used in our study[22].

Alanine transaminase (ALT). ALT is an enzyme found in the liver that helps convert proteins into energy for the liver cells. When the liver is damaged, ALT is released into the bloodstream and levels increase. The normal limit for ALT at MGH is 7 to 55 U/L[23, 24]. The standard deviation for ALT is 12 U/L[23, 24].

Aspartate transaminase (AST). AST is an enzyme that helps metabolize amino acids. Like ALT, AST is normally present in blood at low levels. An increase in AST levels may indicate liver damage, disease or muscle damage. The normal limit for AST at MGH is 10 to 40 U/L. The standard deviation for AST is 7.5 U/L.

Alkaline phosphatase (ALP). ALP is an enzyme found in the liver and bone and is important for breaking down proteins. Higher-than-normal levels of ALP may indicate liver damage or disease, such as a blocked bile duct, or certain bone diseases. The normal limit for ALP at MGH is 45 to 115 U/L. The standard deviation for ALP is 17.5 U/L.

The power calculations shown below are based on paired non-inferiority testing assuming no mean difference between pre and post imaging liver function tests and a non-inferiority margin of 1σ (1/2 upper limit of normal) with alpha = 0.05, target power = 0.9, and an assumed dropout rate of 25%[25]. For comparison, many drug trial use 5x the upper limit of normal as the criteria for drug hepatotoxicity. Our non-inferiority margin has been selected to be much more stringent given that ultrasound is an otherwise noninvasive diagnostic test.

Non inferiority margin	Assumed difference in mean	Standard deviation of biomarker	Sample size	Sample size + Dropout rate (25%)
$1\sigma = 12$	0	$1\sigma = 12$	18	24

10. Monitoring and Quality Assurance

a) Data integrity

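### Standard SWE is scanned first and increased-output SWE second in every subject, so Aim 2 cannot separate the effect of output from the effect of exam order

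*Combined protocol and SAP*

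**What the plan says.** Section 6, Study Visit 1, describes the imaging as follows: "Subjects will then undergo a conventional standard of care ultrasound SWE exam of the liver and a repeat exam with increased acoustic output". For the standard exam, which needs 10 diagnostic values, "If non-diagnostic values are obtained, repeat acquisitions are attempted up to a total of 20 imaging attempts". For the increased-output (CIO) exam, "10 SWE measurements will be repeated in a similar fashion, with 20 acquisition attempts allowed". The data-collection table in Section 6(c) marks both exams at V1 and at no other visit.

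The comparison these exams serve is in Section 2: "Aim 2: Determine if SWE image quality improves when using increased acoustic output". Section 1 ranks it below the safety question: "Secondarily, we aim to understand the degree to which SWE imaging results have improved with the use of COI". The hypothesis in Section 2 joins the two, predicting better image quality without hepatic bioeffects.

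Section 9 deals only with ALT, AST and ALP: "The power calculations shown below are based on paired non-inferiority testing assuming no mean difference between pre and post imaging liver function tests". It gives no image-quality endpoint, test, effect size or power. Section 3 calls the study single arm, and no section mentions randomised, alternating or counterbalanced exam order.

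**The concern.** Each subject is their own control for Aim 2, which is efficient only if the two exams differ in output and nothing else. As Visit 1 is written, they also differ in position: the CIO exam is always the second.

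Position could matter in either direction.

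- **In favour of CIO.** By the second exam the operator may have found the acoustic window and the subject may have practised the breath-holds. Section 6(d) notes that "exams may be performed by research staff who are not credentialed at MGH to perform clinical ultrasound elastography scanning", so some within-subject learning is credible.
- **Against CIO.** Up to 20 attempts at standard output come first, and Section 7(a) lists "the need for repeated breath holding" among the discomforts, so fatigue is also credible.

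An apparent gain could therefore be an order effect, and a real gain could be hidden by one. What is at stake is the image-quality half of the hypothesis. The liver-test comparison is not at stake, because both exams are finished before the day 1 blood draw.

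**Working it through.** **1. The plan's own figure.** The only sample size stated is for Aim 1. With margin 12, SD 12, true difference 0, one-sided alpha 0.05 and power 0.90:

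n = 2 × (1.645 + 1.282)² × (12/12)² = 17.13, rounded up to 18; then 18 / (1 − 0.25) = 24.

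Both figures reproduce. They concern liver tests and say nothing about Aim 2.

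**2. The structural point, which needs no assumption about size.** Let τ be the output effect and π the effect of being scanned second.

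- Standard first in everyone: CIO − standard = τ + π. The design matrix for mean, output and order has rank 2 for 3 parameters, so τ cannot be estimated separately at any sample size.
- Both orders used: second − first is π + τ in one group and π − τ in the other. Half the difference between the groups is τ. The rank is 3.

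**3. Size, without choosing an endpoint.** This is a noncentral t calculation for a paired two-sided 5% test with τ = 0. The order effect is in units of the SD of the paired difference and is assumed.

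| Order effect (SD) | 0 | 0.2 | 0.3 | 0.5 | 0.8 |
|---|---|---|---|---|---|
| False difference, n = 18 | 5% | 13% | 23% | 52% | 89% |
| False difference, n = 24 | 5% | 16% | 29% | 65% | 96% |

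With half the subjects in each order, simulation at 0, 0.3, 0.5 and 0.8 SD keeps the rate at 4.6% to 5.1%.

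**4. Size on a concrete endpoint.** All inputs here are assumptions except the stopping rule, which is the protocol's: an exam ends at 10 diagnostic values or 20 attempts.

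- Endpoint: proportion of attempts that are diagnostic, with a 60% baseline.
- Between-subject SD 0.8 on the logit scale; extra exam-to-exam logit SD within a subject of 0, 0.4 or 0.8.
- Effects in percentage points are converted to logit shifts at the baseline. For example, +10 points is logit(0.70) − logit(0.60) = 0.44.
- Paired t test, one-sided 0.025, n = 24, 20,000 simulated trials per cell.

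False CIO superiority with fixed order and no true CIO effect:

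| Second-exam advantage | 0 | 2 points | 5 points | 10 points | 15 points |
|---|---|---|---|---|---|
| Exam SD 0 | 2.6% | 7% | 25% | 73% | 97% |
| Exam SD 0.4 | 2.5% | 6% | 17% | 54% | 89% |
| Exam SD 0.8 | 2.6% | 5% | 11% | 30% | 61% |

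At n = 18 the 10-point column becomes 60%, 42% and 23%. With randomised order and order as a factor, every cell lies between 2.2% and 2.8% (n = 18 and 24; baselines 40%, 60% and 80%).

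The opposite direction is a true 10-point CIO gain with a 5-point second-exam loss:

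| Power, n = 24 | Fixed, no order effect | Fixed, 5-point loss | Randomised, 5-point loss |
|---|---|---|---|
| Exam SD 0 | 73% | 29% | 75% |
| Exam SD 0.4 | 54% | 20% | 55% |
| Exam SD 0.8 | 30% | 12% | 31% |

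**5. Sensitivity to the endpoint.** If the endpoint is instead whether 10 diagnostic values were reached, a 10-point order effect gives 34% (exam SD 0) or 17% (exam SD 0.8) at a 60% baseline. At an 80% baseline it gives 2% or 14%. On the proportion endpoint a higher baseline does not help: at 80% and exam SD 0 the rate is 91%.

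**The case against.** - **The modelled test is not in the plan.** Section 1 speaks of the degree of improvement, which is estimation language, and Section 9 tests only liver enzymes. This stands: the error rates translate an assumed order effect into a test that the plan does not specify. The firm statement is that any estimate carries a bias of unknown sign and size. The missing Aim 2 endpoint is itself a documented gap.
- **The size depends on the endpoint.** This stands. Figure 1 presents the imaging problem as poor filling of the measurement region, which was not modelled, and the yes/no endpoint gives smaller figures.
- **The mechanisms are thinly supported.** The credentialing remark explains why results are not released, and breath holding is listed only as a discomfort. Both show that an order effect is plausible; neither shows that one exists.
- **The order is not declared fixed, and Section 1 suggests another sequence.** Fixed order is inferred from the CIO exam being called a repeat. Section 1 also describes a washout and then standard imaging. That sentence concerns liver tests, has no matching visit in Section 6 and would also be a single fixed order. It must be reconciled with Visit 1, but it does not rescue Aim 2.
- **Randomising order does not blind anyone.** The operator sets the output, and no blinded reading is described. This stands as a separate limitation.
- **Aim 2 is secondary.** True, and it limits the weight of the point. It does not make the bias removable after scanning.

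**Conclusion.** The concern holds. As Visit 1 is described, output level and exam order are completely aliased, and the only within-subject comparison available for Aim 2 estimates their sum. This follows from the design alone.

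The practical size is not known. Under the assumptions shown, a 5-point advantage to the second exam raises false superiority from the nominal 2.5% to between 11% and 25%, and a 10-point advantage raises it to between 30% and 73%. A 5-point disadvantage cuts power for a true 10-point gain by more than half. Other endpoints can give much smaller figures.

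The consequence is confined to Aim 2. The Aim 1 liver-test comparison and its 18 and 24 subjects do not change.

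**What to change.** - Randomise the order of the two Visit 1 exams 1:1, in blocks within the four BMI recruitment cohorts of Section 4(c). If cohorts fill equally, 24 / 4 = 6 subjects per cohort, or 3 per order. Order splits of 10/14 or 8/16 still give 2.3% to 2.7% false superiority in the simulation.
- State the Aim 2 endpoint and analysis in Section 9. One option is the within-subject CIO-minus-standard difference in the proportion of attempts that are diagnostic, averaged over the two orders with order as a factor. Define what counts as diagnostic.
- Begin scanning once the screening results that already gate CIO imaging are available.
- If the order must stay fixed, say why, state that Aim 2 cannot attribute a difference to output alone, and log every attempt so that a trend within each exam can be shown. Such a trend would be partial evidence only.

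The cost is an allocation list and one degree of freedom, with no added visit, scan, blood draw or subject. When screening and Visit 1 fall on the same day, the standard exam could no longer be done while results are pending; the CIO exam has to wait for them in either order. Averaging over orders removes an order effect common to both sequences. It does not remove unequal carry-over, such as a window found under CIO helping a later standard exam, and 24 subjects could not test for that well.

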Blood sampling requires needle placement into a peripheral vein which is likely to cause brief minor pain. A small bruise may result. The small volume of blood obtained during the study is unlikely to be of clinical consequence.

b) Drug side effects and toxicities

Not applicable

c) Device complications/malfunctions

The images acquired in this study will not be used for clinical decision making; thus, any acquired images with suboptimal image quality should not otherwise affect patient care. Malfunctioning channel elements may reduce image quality, however the malfunction would be expected to lead

to less energy deposition with a subject, and thus less risk of tissue injury, which is already considered low. Significant complications from peripheral venous blood sampling would be unusual.

d) Psychosocial (non-medical) risks

There is a small risk of loss of confidentiality, however strict measures are followed to maintain confidentiality. The data being acquired and analyzed is not considered sensitive.

e) Radiation Risks (statement provided by Radiation Safety Committee)

Ionizing radiation is not used for this study.

f) Risk Reduction

Energy levels selected for increased acoustic output SWE acquisition are based on prior human study and expert opinion and are likely to be safe. The target study population will be selected such that subjects are of generally good health and would be expected to tolerate small amounts of liver damage were it to occur without catastrophic consequences. Subjects will be carefully screened and excluded if active/ongoing significant liver injury is present to prevent the additive effects of the investigational technology. Pregnant women are excluded from this study as the risks to an embryo or fetus from increased acoustic output ultrasound are unknown. Subjects will be carefully monitored throughout the study with serial lab testing to assess early and late hepatic effects from increased acoustic output SWE. Subjects will be enrolled in EPIC in order to capture unanticipated hospital visits that could be related to the intervention. Frequent E-PAT testing will be performed to identify probe malfunctions at the channel level. Such hardware failures would result in a pause to enrollment while hardware repair or replacement occurred in order to maximize image quality and scientific benefit from each subject. Such a malfunction is not expected to increase risk as energy deposition is expected to be lower.

8. Benefits

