A unique source record will be available for each study subject including completed Informed Consent Forms, eligibility assessment, social security number, laboratory values, and all records related to ultrasound imaging of the subject. The PI will designate a physician study staff member to review data entries at least quarterly to assess for data completeness and regulatory compliance.

At the time of enrollment, subjects will be assigned a study number that will be the only identifier included on study documents, aside from the consent form, Rally volunteer list, and payment information form that includes subject social security numbers for subject compensation. Blood specimens will be obtained, labelled, and handled per standard clinical routine by MGH outpatient phlebotomy services. Subject name and study number will be saved

in a single file on an MGB server running antivirus software. Access will be restricted to MGB study staff and will not be shared beyond MGB. All remaining data will be stored separately using only subject number to identify data. Printed study documents will be stored in a secure cabinet in a locked office at the Center for Ultrasound Research and Translation (CURT). Only MGB study investigators and staff will have access to study files. Data shared with collaborators will not include identifiable information. Confidentiality of subjects will be strictly protected. The investigators will comply with the human subject investigation guidelines of Massachusetts General Hospital

b) Safety monitoring

Safety monitoring will be performed by study staff members and the PI; the PI will be responsible for overall monitoring. Subject safety will be monitored by research staff to detect any changes in health status from enrollment. Subject safety will be monitored from the time each subject signs the Informed Consent Form until completion of study participation. Subjects will have available the contact information of study personnel should an adverse event occur following the study visit. The PI will be notified within 24 hours of potential adverse events including any laboratory value outside of the normal range.

c) Outcomes monitoring

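### No post-scan liver test result, at any grade, obliges increased-output scanning to pause; a reversible hold above 3x ULN would be a cheap, optional safety addition

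*Combined protocol and SAP*

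**What the plan says.** All references are to the combined protocol and SAP.

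- **6f, Study Termination Criteria.** The liver-test and pregnancy criteria are "Subjects with baseline liver function testing values greater than 3x the laboratory upper limit of normal or with a positive serum pregnancy test". Such subjects get neither the increased-output scan nor follow-up liver tests. The section's only other rule defines loss to follow-up.
- **6a and 6b.** Each subject has one increased-output session, at Visit 1, within 48 hours of the screening blood draw. Liver tests follow at 1, 2 and 7 days. On output: "An MI of 2.9 will be used for CIO".
- **6d, Result Reporting.** "Subjects will be contacted by the study team for lab values higher than 3x the laboratory upper limit of normal". No study-level step follows.
- **7f, Risk Reduction.** The one prespecified pause is for probe failure: "Such hardware failures would result in a pause to enrollment while hardware repair or replacement occurred". The protocol adds that this malfunction is not expected to raise risk.
- **8, Benefits.** "There are no expected direct benefits to the subjects participating in the study".
- **10b, Safety monitoring.** "The PI will be notified within 24 hours of potential adverse events including any laboratory value outside of the normal range".
- **10c, Outcomes monitoring.** It defines four grades, including "grade 2 = 3-5x upper limit of normal; grade 3 = 5-20x upper limit of normal". The draws are there to follow the trend and to see whether values normalise.
- **10d, Adverse event reporting.** Each event is assessed for severity, relatedness and action taken, and is reported under IRB guidelines. "The principal investigator will review adverse events on an individual basis".

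**The concern.** Aim 1 asks whether output above the FDA limits causes hepatic bioeffects, so a post-scan rise in liver enzymes is the event the study is built to detect. The protocol grades that event but does not say which grade, if any, stops the next scan. The only pause it prespecifies is for a fault it regards as harmless to the subject.

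At stake is the safety of subjects not yet scanned. They expect no direct benefit and are exposed at an MI of 2.9, against 1.9 in the FDA guidance cited in section 1a. Without a threshold, the decision to continue is made after the result is seen, by the person responsible for the study. Section 7f presents serial laboratory testing as a risk-reduction measure. With one exposure per subject, testing can reduce exposure only for later subjects, and only if results feed back into further scanning.

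**Working it through.** **1. The plan's own figure.** Section 9 gives margin 12, SD 12, assumed difference 0, alpha 0.05, power 0.9 and dropout 25%. Taking alpha as one-sided and the SD of a paired difference as √2 × 12:

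n = (1.645 + 1.282)² × 2 × 12² / 12² = 17.1, rounded up to 18; 18 / 0.75 = 24.

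The stated 18 and 24 reproduce, and nothing below changes them.

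**2. Is there a trigger anywhere?** Responses to an abnormal post-scan value, side by side:

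| Section | Condition | Required response | Pause in scanning? |
|---|---|---|---|
| 6d | above 3x ULN | contact the subject | no |
| 10b | outside normal range | tell the PI within 24 hours | no |
| 10c | grades 1 to 4 | grade and trend | no |
| 10d | any adverse event | PI assessment; reporting under IRB guidelines | none stated |
| 6f | baseline above 3x ULN | no increased-output scan for that subject | not a post-scan rule |

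No row ties a post-scan value to a hold.

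**3. What 3x ULN means.** From the section 9 limits: ALT 3 × 55 = 165, AST 3 × 40 = 120, ALP 3 × 115 = 345 U/L. From the ULN, an ALT rise of 165 − 55 = 110 U/L is needed, about 9 of the stated 12 U/L SDs (110 / 12 = 9.2).

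**4. Upper bound on benefit.** The documents give no event rate, so p, the chance of a grade 2+ result per scanned subject, is assumed. Suppose each result is known before the next scan, scanning would otherwise run to 24, and the hold is never lifted. Then:

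- expected number scanned = (1 − (1 − p)^24) / p
- subjects not scanned = 24 minus that
- events averted = p × subjects not scanned

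| p | Scanned | Not scanned | Events averted |
|---|---|---|---|
| 0.1% | 23.73 | 0.27 | 0.0003 |
| 1% | 21.43 | 2.57 | 0.026 |
| 5% | 14.16 | 9.84 | 0.49 |
| 10% | 9.20 | 14.80 | 1.48 |

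If 3 more subjects are scanned before the first result is seen, the sum over i = 1 to 24 of (1 − p)^(i−1) × p × max(0, 24 − i − 3) gives 0.21, 1.97, 7.81 and 12.09 not scanned. Multiplied by p, that is 0.0002, 0.020, 0.39 and 1.21 events averted.

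**5. Unrelated holds.** With an assumed background rate b per subject, P(at least one hold) = 1 − (1 − b)^24 = 2.4% at b = 0.1% and 21.4% at b = 1%. With 18 subjects giving post-scan samples, these are 1.8% and 16.5%.

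**The case against.** The strongest reply is that oversight already exists. The PI learns of any out-of-range value within 24 hours, judges relatedness and action taken, and reports to the IRB, whose guidelines are not in the documents and might themselves constrain continuation. That stands. A reader might infer that the study has no safety monitoring, or that scanning would run on regardless of harm; the documents do not support either. They show only that no threshold is written down. That continuation is a matter of judgement is itself an inference, from the PI's overall monitoring responsibility and the lack of a stated trigger.

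The risk may also be very low. Section 7a calls the potential for cavitation very small and cites a report that in situ values up to 4.0 could be justified where there is clinical benefit. Section 7f says the energy levels rest on prior human study and expert opinion. This too stands, and it is why the low assumed rates deserve most weight.

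Finally, the trigger is a choice. A hold above 3x ULN ignores grade 1: an ALT going from 20 to 160 U/L would not set it off. Holding at the second event would cut unrelated holds at a 1% background rate from about 21% to about 2%, but would react later. What favours a single event above 3x ULN is that sections 6d and 6f already use that level, so no new cut-off is introduced.

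**Conclusion.** The gap is real and modest. As written, no grade and no post-scan value requires increased-output scanning to pause, and continuing after a grade 2 or higher result rests on case-by-case judgement. Closing it is an optional improvement in patient safety. No stated figure or planned analysis is wrong or would change.

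At assumed rates of 0.1% to 1%, a hold averts at most about 0.0003 to 0.03 grade 2+ events per 24-subject trial. Even that is an upper bound, because the PI or IRB might pause anyway and the hold can be lifted. It is tempting to cite the 10 to 15 subjects who would go unscanned at rates of 5% or 10%. Those rates have no source in the documents and sit poorly with section 7a. The count also measures exposures, not injuries, and assumes nobody would otherwise intervene.

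The case for the change therefore rests on the principle of fixing the response before the result is seen, at low cost, and not on a large expected saving.

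**What to change.** Add to 6f:

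*If any subject has a post-scan ALT, AST or ALP above 3x ULN (10c grade 2 or higher), no further increased-output scans are performed until the PI has reviewed the event, including its relatedness, reported it to the IRB, and the IRB has agreed to resume.*

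No exception for a high baseline is needed, since 6f already keeps subjects above 3x ULN at baseline from the scan and from follow-up tests. The relatedness review deals with other causes; section 9 notes that AST can rise with muscle damage and ALP with bone disease.

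The cost is one sentence by amendment, plus a PI and IRB review for each hold, of a duration the documents do not give. It is not free for the schedule. Section 6a requires Visit 1 within 48 hours of the screening draw, so a subject screened but not yet scanned may need a repeat draw or visit if the hold outlasts that window. Subjects scanned before a result comes back are not protected, and no stagger between subjects is proposed.
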